2.1. Name of Project

CLINICAL OUTCOMES OF AUTONOMOUS CORTISOL SECRETION IN ADRENAL INCIDENTALOMAS.

2.2. Scientific context

The natural history of adrenal incidentalomas is largely unknown. A number of recent studies have provided evidence for an increased rate of cardiovascular (CV) events and mortality in patients with adrenal incidentalomas and autonomous cortisol secretion. However, evidence comes from limited patient cohorts with rather short follow-up. Furthermore, a heterogeneous definition of autonomous cortisol secretion hampered to recognize which levels of functional autonomy are associated to increased morbidity and/or mortality.

2.3. Aim

The primary aim of the study is to assess mortality, CV events and the rate of vascular and metabolic comorbidities potentially linked to cortisol excess (hypertension, diabetes, dyslipidemia, obesity) in patients with adrenal incidentalomas and calculate HRs for patient groups stratified by cortisol values following the 1-mg overnight dexamethasone test.

Two types of CV events are differentiated:

- ‘major CV events’: clinically symptomatic myocardial infarction or stroke followed by hospitalization, or CV-related death.
- ‘minor CV events’: any other type of myocardial infarction and therapeutic procedures for coronary heart disease (PTCA, surgical bypass), any stroke, transient ischemic attack, heart failure, deep vein thrombosis, pulmonary embolism.

CV events are optimally registered by hospital medical records reporting one (or more) of the followings: acute myocardial infarction and related therapeutic procedures (PTCA, surgical bypass), stroke, TIA, heart failure, deep vein thrombosis, pulmonary embolism, sudden death, or death from cardiovascular cause.

However, it will be allowed to obtain data with telephonic interview using a structured questionnaire aimed to recognize the presence of the above-mentioned comorbidities and the occurrence of major CV events (clinically symptomatic myocardial infarction, stroke, death).

We will assess:

- Overall Survival (OS) as primary endpoint, defined as the time interval between the date of discovery of adrenal incidentaloma and the date of death from any cause, in patients stratified by different cortisol cut-offs.
- Event-free Survival (ES), defined as the time interval between the date of discovery of adrenal incidentaloma and the date of occurrence of a 'major' and/or 'minor' CV event, in patients stratified by different cortisol cut-offs.
- CV mortality, defined as death from any CV cause, in patients stratified by different cortisol cut-offs. Other causes of death will be specified, as well.

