2.4. Methods

Retrospective, multi-center study

CV events are optimally registered by hospital medical records or can be obtained with telephonic interview using a structured questionnaire aimed to recognize the presence of the above-mentioned comorbidities and the occurrence of CV events.

Statistical analysis:

CV event rates will be expressed as the number of events per 1000 person-years.

Kaplan-Meier analysis will be used to construct survival curves and compute risks. Cox regression will be used for time-to-event analysis, and hazard ratios (HRs) computed with accompanying 95% confidence intervals (95% CI). Analysis will be stratified according to post-dexamethasone cortisol levels with three pre-specified cutoffs: ≤ 50 nmol/L (1.8 μ g/dL), 51-138 nmol/L (1.9-5.0 μ g/dL) and > 138 nmol/L (> 5 μ g/dL). However, additional cutoffs might be analysed as well.

Depending on the level of comprehensive documentation of the patients' characteristics two cohorts will be separately analysed:

- Cohort A: all requested data are available
- Cohort B: patients with missing data, but the following data are available: date of diagnosis the adrenal incidentaloma, result of 1mg DST, and survival status (or date of death).

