2.5. Requested clinical annotations (type, justification)

Inclusion criteria:

- Age ≥ 18 years
- Adrenal mass detected by sensitive imaging tests (CT or MRI) not done for suspected adrenal disease since 1-1-2000 (modified in Oct 2018 to 1-1-1996 to allow longer follow-up time)
- Imaging characteristics typical of adrenal adenoma: unenhanced or delayed enhanced CT, MRI with chemical shift and FDG-PET are all acceptable to secure this diagnosis.

- In the absence of appropriate imaging study, results of 12-month follow-up showing unchanged mass characteristics can be considered as surrogate criterion.
- Availability of 1-mg overnight dexamethasone test results done at diagnosis or during follow-up
- Follow-up duration of at least 36 months (from the date of diagnosing the adrenal mass the first time)
- Availability of follow-up data on living status and occurrence of CV events (telephone interview allowed to capture data)

Exclusion criteria:

- Presence of clinical features of overt Cushing's syndrome
- UFC $\geq 2 \times$ ULN
- ACTH-dependent Cushing syndrome
- Any active malignancy

Minimum clinical annotations:

- Date of birth, date of diagnosis
- Imaging characteristics (mass size, density on unenhanced CT (HU units), absolute or relative wash-out on delayed enhanced CT, results of MRI with chemical shift, results of FDG-PET, or imaging during follow-up > 12 months after initial imaging demonstrating unchanged tumor size)
- Serum cortisol following 1-mg DST, UFC, plasma ACTH (only serum cortisol after dexamethasone will be entered into the statistical model)
- Presence of obesity, hypertension, diabetes, dyslipidemia at initial diagnosis
- Information on prevalent CV events
- Date of last follow-up (date of death)
- Presence of obesity, hypertension, diabetes, dyslipidemia at last follow-up
- Information on incident CV events and date of first event

Minimum expected patient cohort per center: 50

Data acquisition via ENS@T registry

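### Section 2.3 confines the telephone questionnaire to major CV events while sections 2.4 and 2.5 do not; if 2.3 is followed, ascertainment of event-free survival depends on the follow-up source

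*Combined protocol and SAP*

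**What the plan says.** All references are to the combined protocol and SAP.

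- **Endpoint.** Section 2.3 defines ES as the time from discovery of the incidentaloma to "the date of occurrence of a 'major' and/or 'minor' CV event". Major events are "clinically symptomatic myocardial infarction or stroke followed by hospitalization, or CV-related death". Minor events are other infarctions, coronary procedures and "any stroke, transient ischemic attack, heart failure, deep vein thrombosis, pulmonary embolism".
- **Telephone route, section 2.3.** Hospital records are the preferred source, but a telephone questionnaire is allowed. It covers comorbidities and "the occurrence of major CV events (clinically symptomatic myocardial infarction, stroke, death".
- **Telephone route, section 2.4.** What appears to be the same instrument is a "structured questionnaire aimed to recognize the presence of the above-mentioned comorbidities and the occurrence of CV events". The word major is absent.
- **Telephone route, section 2.5.** The inclusion criterion reads "Availability of follow-up data on living status and occurrence of CV events (telephone interview allowed to capture data", again without a limit to major events.
- **Data items, section 2.5.** For outcomes, the minimum annotations ask for "Information on incident CV events and date of first event". Neither the source of follow-up nor the scope of the questionnaire is listed.
- **Cohorts, section 2.4.** Patients are split by completeness: "Cohort A: all requested data are available", against Cohort B, which has missing data but a known diagnosis date, dexamethasone test result and survival status. No analysis by source of follow-up is described.

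**The concern.** Section 2.3 is narrower than 2.4 and 2.5. A centre working from 2.3 and a centre working from 2.4 would ask their telephone patients different questions.

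This matters for ES and for the CV event rates per 1000 person-years, because both include minor events. Under 2.3, whether the same heart failure admission counts can depend on how the patient was followed up. Event rates would then be too low. If the loss is not the same in each cortisol group, part of any ES difference between groups would reflect ascertainment rather than cortisol. Without a record of source and scope, nobody could tell afterwards whether that had happened.

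**Working it through.** **Step 1. What each route covers under section 2.3.**

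| Event | Class | Hospital-record list | Telephone list |
|---|---|---|---|
| Symptomatic MI, hospitalised | major | yes | yes |
| Stroke, hospitalised | major | yes | yes |
| Stroke, not hospitalised | minor | yes (any stroke) | possibly; stroke is unqualified |
| TIA, heart failure, DVT, PE | minor | yes | no |
| Coronary procedures | minor | those related to acute MI | no |
| Death | major if CV-related | sudden or CV death | yes; cause not specified |

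The contrast is firmest for TIA, heart failure, DVT and PE. The telephone list also differs from the section's own definition of a major event: it drops the hospitalisation condition on stroke and the CV condition on death.

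**Step 2. Effect on event rates.** There is no figure in the documents to reproduce. Let p be the share of patients followed by telephone only and m the fraction of first ES events that telephone follow-up misses. Both are assumed here: p from 10% to 50%, m from 20% to 60%, and no events missed by records.

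Understatement of the rate ≈ p × m:

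- 0.1 × 0.2 = 2%
- 0.3 × 0.2 = 6%
- 0.3 × 0.6 = 18%
- 0.5 × 0.6 = 30%

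These are approximate upper bounds. A patient with a missed minor event who later reports a major one still counts, but with a date that is too late.

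**Step 3. Effect on the hazard ratio.** With a true HR of 1 for the highest against the lowest cortisol group:

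observed HR ≈ (1 − p_high × m_high) / (1 − p_low × m_low)

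| p low / high | m low / high | Observed HR | Low and high swapped |
|---|---|---|---|
| 0.3 / 0.3 | equal | 1.00 | 1.00 |
| 0.3 / 0.3 | 0.2 / 0.6 | 0.82/0.94 = 0.87 | 1.15 |
| 0.1 / 0.1 | 0.2 / 0.6 | 0.94/0.98 = 0.96 | 1.04 |
| 0.4 / 0.2 | 0.4 / 0.4 | 0.92/0.84 = 1.10 | 0.91 |
| 0.4 / 0.2 | 0.3 / 0.6 | 0.88/0.88 = 1.00 | 1.00 |

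The last row shows that only the product p × m has to match between groups. Share and missed fraction can each differ and still cancel.

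**Step 4. Would a simple analysis adjustment cure it?** This was simulated with 10 runs of 20,000 patients per group, true HR 1, an assumed 15 events per 1000 person-years, 3 to 15 years of follow-up, and Monte Carlo error of about 0.01.

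- *Stratifying the Cox model by source.* When only the share differs (fourth row above), the HR goes from 1.11 unstratified to 1.01. When the missed fraction differs (second row), it stays at 0.87, because the HR within the telephone stratum is itself about (1 − 0.6)/(1 − 0.2) = 0.50.
- *Restricting to patients with records.* This works if having records is unrelated to having had an event (HR 1.01). Suppose instead that records exist for 70% of everyone in the lowest group, but in the highest group for 90% of patients with an event and 60% of those without. The HR then reads 1.45; the rare-event approximation is (0.9/0.6)/(0.7/0.7) = 1.5. With 90% and 60% in both groups the HR is about 1.0, but the rate reads about 22 instead of 15.

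**The case against.** The case on the other side is substantial.

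- **The sections do not all conflict with one another.** Sections 2.4 and 2.5 agree, and they are the operational ones. If they govern, and CV events there means major and minor as in 2.3, the scope problem does not arise. This stands, and it makes every consequence conditional on 2.3 being followed. It does not remove the need to reconcile the text: the questionnaire is not in the documents, and 2.3 is explicit.
- **The cohort split may already help.** A reader might infer that telephone-only patients sit in Cohort A because an answer of no event fills the incident-event item. The documents do not say so. A patient never asked about minor events could equally be judged to lack requested data and go to Cohort B. Even then, Cohort B would mix such patients with those missing anything else, so the split does not clearly isolate them.
- **The source may be recorded anyway.** The annotations are a minimum, and data come through a registry whose fields are not shown. A reader might infer that source, scope and the date of a first major event are not captured at all. The documents support only that they are not listed.
- **The sizes are assumed.** This is correct. Telephone contact may only supplement records, and a threefold difference in missed fraction has no basis in the documents.

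**Conclusion.** The inconsistency is real: section 2.3 against sections 2.4 and 2.5. If 2.3 is followed, ascertainment of minor events depends on the follow-up source. Event rates are then understated by at most about p × m, which is 2% to 30% over the assumed ranges. The ES hazard ratio is biased if p × m differs between cortisol groups; with a true HR of 1, the assumed contrasts above give 0.87 to 1.15.

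Two stronger readings are not supported. One is that the ES hazard ratio is biased: the documents give neither the telephone-only share nor the missed fraction, so presence, direction and size are all unknown. The other is that the ratio is sound only if share and missed fraction are each equal across groups: equality of their product is enough.

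Overall survival, the named primary endpoint, is not affected, because death is captured by either route. The point concerns ES and the CV event rates. It should be addressed, but it does not undermine the main endpoint.

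**What to change.** 1. Reconcile section 2.3 with 2.4 and 2.5 so that the questionnaire asks about every ES component, with major events defined exactly as in 2.3, including the hospitalisation and CV-death conditions.
2. Record for every patient, with or without an event, which source was searched (records, telephone or both) and whether minor events were asked about.
3. Keep all patients in the main ES analysis.
4. Add a major-events-only analysis in all patients. This needs the date of the first major event, to be collected if the registry does not already hold it.
5. Add, as a sensitivity analysis only, ES limited to patients with records or full-scope interviews. State that it can itself be selected if record availability depends on having had an event. Because of that risk, excluding major-only telephone patients should not replace the main analysis. Stratifying by source is at best a partial remedy.

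**Cost.** Questionnaire wording and a few registry fields, possible re-contact of patients already interviewed close to the November 2018 data deadline in section 2.8, and fewer patients in the restricted analysis.

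### ES and the CV event rate include patients with CV disease before discovery, and the analysis makes no use of the prevalent CV events that are collected, so the crude ES HR is open to confounding

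*Combined protocol and SAP*

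**What the plan says.** - **Endpoint (2.3 Aim).** "Event-free Survival (ES), defined as the time interval between the date of discovery of adrenal incidentaloma and the date of occurrence of a" major or minor CV event. The definition is not limited to patients free of CV disease at discovery or to a first-ever event. Minor events cover "any other type of myocardial infarction and therapeutic procedures for coronary heart disease (PTCA, surgical bypass), any stroke, transient ischemic attack, heart failure" and venous thromboembolism.
- **Analysis (2.4 Methods).** "CV event rates will be expressed as the number of events per 1000 person-years". Kaplan-Meier curves and Cox HRs are planned by three bands of post-dexamethasone cortisol. Prior CV events appear neither as a covariate or stratum nor in an at-risk definition. The only other split, Cohort A against Cohort B, is by completeness of data.
- **Eligibility (2.5).** There are four exclusion criteria: "Presence of clinical features of overt Cushing's syndrome", raised urinary free cortisol (UFC), ACTH-dependent disease and active malignancy. Prior CV disease is not one of them.
- **Data items (2.5).** Two separate items are requested: "Information on prevalent CV events" and "Information on incident CV events and date of first event". No section says how the first is used.

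**The concern.** The cortisol bands are observed, not randomised, so they may differ in CV history. A patient with earlier CV disease can be expected to have a higher hazard of a further event. If such patients are more common in one band, that band's ES hazard is higher even where cortisol has no effect on later events. Section 2.2 cites evidence linking autonomous cortisol secretion to CV events, so an imbalance in CV history is plausible, although the documents do not show one.

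At stake is how the ES HR and the event rates can be read. The plan does not say whether an HR above 1 for the highest band would mean more new CV disease, more recurrence in patients already ill, or both. Centres also have no common rule for a continuing condition, heart failure above all, that was present at discovery and is recorded again later.

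**Working it through.** **Is there a figure to reproduce?** No. The plan gives no event count, effect size, power or prevalence of prior CV disease. What follows is an illustration on assumed inputs.

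**Step 1. Who is at risk for ES?** Prior CV disease is not excluded (2.5), a data item for it is requested (2.5), and nothing in 2.3 or 2.4 removes these patients. The plain reading is that they stay in the risk set.

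**Step 2. Confounding of the crude HR.** Let p0 and p1 be the shares with prior CV disease in the lowest and highest bands, and h the hazard ratio for prior disease. With no cortisol effect, the crude rate ratio, which approximates the HR early in follow-up, is

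(1 - p1 + p1·h) / (1 - p0 + p0·h)

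With p0 = 10%:

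| h | p1 = 15% | p1 = 20% | p1 = 25% |
|---|---|---|---|
| 2 | 1.15/1.10 = 1.045 | 1.20/1.10 = 1.091 | 1.25/1.10 = 1.136 |
| 3 | 1.30/1.20 = 1.083 | 1.40/1.20 = 1.167 | 1.50/1.20 = 1.250 |
| 4 | 1.45/1.30 = 1.115 | 1.60/1.30 = 1.231 | 1.75/1.30 = 1.346 |

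The range is 1.05 to 1.35. If p1 = p0 = 10%, the ratio is 1.00 for any h. If prior disease were rarer in the highest band, say p1 = 5% with h = 3, the ratio would be 1.10/1.20 = 0.92. The direction therefore depends on the imbalance.

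**Step 3. Event rates.** On the same inputs, a band's overall rate is (1 - p + p·h) times the rate in its patients without prior disease: 1.10 at p = 10% and h = 2, and 1.75 at p = 25% and h = 4. The overall rate is therefore not a first-event incidence.

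**Step 4. Miscounting old disease as new.** ES time starts at discovery, so an event dated earlier is not an ES event, and 2.5 keeps prevalent and incident events apart. That leaves continuing conditions and telephone reports whose date cannot be placed before or after discovery. Let f be the share of patients with prior disease wrongly counted as incident, and r0 and r1 the true risks in the two bands. The risk ratio is

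[r1 + (1 - r1)·f·p1] / [r0 + (1 - r0)·f·p0]

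- No true effect (r0 = r1 = 10%), p0 = 10%, p1 = 20%: f = 5% gives 0.109/0.1045 = 1.04; f = 10% gives 0.118/0.109 = 1.08; f = 20% gives 0.136/0.118 = 1.15.
- True ratio 1.5 (r0 = 10%, r1 = 15%), p0 = p1 = 10%: f = 5% gives 0.15425/0.1045 = 1.48; f = 20% gives 0.167/0.118 = 1.42.

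Miscounting can thus raise or lower the ratio.

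**The case against.** The strongest case against has five parts.

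1. **Old and new events are already separated.** A reader might infer that old disease is generally counted as new. The documents do not support this: section 2.5 records prevalent and incident events as different items, and ES counts only from discovery. The statement in 2.3 about hospital records names a preferred source; it is not a rule that dates an event at its first mention. A coronary procedure performed after discovery is a genuine new event, listed on purpose. Only the residual risk in step 4 remains.
2. **Keeping these patients is legitimate.** Time from discovery to the next CV event is a well-defined quantity in patients with or without a history. This stands: retention is not in itself an error. What is missing is any use of the history in the comparison.
3. **Prior CV disease may partly result from cortisol excess before discovery.** Stratifying on it, or restricting to patients without it, may then remove part of the effect of interest. This also stands, so the stratified result should not replace the unstratified one.
4. **Some patients may lack the item.** Cohort B needs only the diagnosis date, the dexamethasone test result and survival status. Such patients may have no prevalent CV information, so a stratified model can lose some of them.
5. **The list of model variables may not be closed.** A reader might take "only serum cortisol after dexamethasone will be entered into the statistical model" as ruling out every covariate. The remark is attached to the line on hormone tests and may do no more than set aside UFC and ACTH. The point rests instead on 2.4 naming no role for prior CV events.

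**Conclusion.** The point holds in a limited form. Patients with prior CV disease are eligible and stay at risk for ES and the event rate, and the stated analysis ignores a baseline item that the study collects. Followed as written, the ES HR is confounded whenever prior CV disease differs by cortisol band.

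The 1.05 to 1.35 range rests wholly on assumed prevalences and an assumed hazard ratio for prior disease. A reader might infer that the plan's ES HR is inflated by this amount. The documents do not support that: they give no data on CV history by band, and balanced history would leave no confounding. Nor can it be said that miscounting adds to any inflation, since it can also pull the ratio down.

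OS, the primary endpoint, is death from any cause. How CV events are classified does not change it, and this point makes no claim about it.

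**What to change.** Add to section 2.4:

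> ES Cox models use a baseline hazard stratified by prevalent CV event at discovery (yes/no). The unstratified HR is reported beside it, because prior CV disease may partly reflect cortisol exposure before discovery. Kaplan-Meier curves and rates per 1000 person-years are shown overall and separately for patients with and without a prevalent CV event; only the results in patients without one are described as first-event incidence. A continuing condition already recorded as prevalent (e.g. heart failure) counts as an incident event only if a new dated episode after discovery is recorded. Patients with unknown prevalent CV status (possible in Cohort B) are left out of the stratified model and their number is reported.

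**Cost.** A little more analysis on a variable already requested. Patients with unknown prior status drop out of the stratified model. Over-adjustment is possible, but reporting both HRs makes it visible. The rule for continuing conditions needs the type of prevalent event. Where a first recorded event is disallowed, it also needs the date of the next one; section 2.5 asks only for the first, so centres may have to supply this for a few patients.

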2.4. Methods

Retrospective, multi-center study

CV events are optimally registered by hospital medical records or can be obtained with telephonic interview using a structured questionnaire aimed to recognize the presence of the above-mentioned comorbidities and the occurrence of CV events.

Statistical analysis:

CV event rates will be expressed as the number of events per 1000 person-years.

Kaplan-Meier analysis will be used to construct survival curves and compute risks. Cox regression will be used for time-to-event analysis, and hazard ratios (HRs) computed with accompanying 95% confidence intervals (95% CI). Analysis will be stratified according to post-dexamethasone cortisol levels with three pre-specified cutoffs: ≤ 50 nmol/L (1.8 μ g/dL), 51-138 nmol/L (1.9-5.0 μ g/dL) and > 138 nmol/L (> 5 μ g/dL). However, additional cutoffs might be analysed as well.

Depending on the level of comprehensive documentation of the patients' characteristics two cohorts will be separately analysed:

- Cohort A: all requested data are available
- Cohort B: patients with missing data, but the following data are available: date of diagnosis the adrenal incidentaloma, result of 1mg DST, and survival status (or date of death).

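### The plan has no rule for a CV event that is known but undated. Read literally, Cohort A excludes such patients on an item no event-free patient can fail, which pushes its CV event rates down to the extent that events are undated.

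*Combined protocol and SAP*

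**What the plan says.** - **Endpoint (2.3 Aim).** ES runs from discovery of the adrenal mass to "the date of occurrence of a 'major' and/or 'minor' CV event". Overall survival (OS) is the primary endpoint, but CV events are part of the stated primary aim.
- **Eligibility (2.5).** The criterion is "Availability of follow-up data on living status and occurrence of CV events (telephone interview allowed to capture data"). It does not mention an event date.
- **Telephone route (2.4 Methods).** Where hospital records are not used, data may come from a "structured questionnaire aimed to recognize the presence of the above-mentioned comorbidities and the occurrence of CV events". Dates are not mentioned here either.
- **Requested items (2.5).** The minimum annotations include "Information on incident CV events and date of first event", and a date of last follow-up or death for every patient.
- **Cohorts (2.4).** The rule is that "two cohorts will be separately analysed". The first is "Cohort A: all requested data are available". The second is "Cohort B: patients with missing data, but the following data are available", the required data being diagnosis date, dexamethasone test result and survival status.
- **Analysis (2.4).** CV event rates are per 1000 person-years, with Kaplan-Meier and Cox analyses by cortisol band.

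The documents do not say how a CV event with a partial or missing date is to be handled.

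**The concern.** The data-collection text asks whether an event happened, while the endpoint and the cohort rule need to know when. Discovery may date from 1996 and data acquisition closes in 2018, so an interview may ask a patient to date an event from up to two decades earlier. Some interviews may yield a definite event without a usable date.

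Such a patient is eligible, but a literal reading of the completeness rule moves the patient to Cohort B, where ES as defined still cannot be timed. An event-free patient has no event date to lack. On this one item, entry to Cohort A therefore depends on the outcome being analysed. Events leave the numerator while event-free person-time stays in the denominator.

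At stake are the Cohort A CV event rates and ES curves and, if dating quality differs between cortisol bands, the ES hazard ratio. With no rule in place, the handling would be chosen after the data are seen.

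**Working it through.** The plan states no event rate, sample size or share of undated events, so there is no figure of its own to reproduce. Every input below is an assumption.

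**Formula.** Let E be the number of patients with an event, T1 their person-years to the event, T0 the event-free patients' person-years, and u the share of events that are undated.

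- Full rate = E / (T0 + T1)
- Rate after undated-event patients leave = (1−u)E / (T0 + (1−u)T1)

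The second is lower than the first whenever u > 0 and T0 > 0.

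**Simple case.** Take 1000 patients, 10% with an event, 7 years of follow-up if event-free and 3.5 years to the event otherwise. Then E = 100, T0 = 900 × 7 = 6300 and T1 = 100 × 3.5 = 350. The full rate is 100/6650 = 15.04 per 1000 person-years.

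| u | Undated-event patients leave Cohort A | Change | Kept, event placed at last follow-up | Change |
|---|---|---|---|---|
| 5% | 95/6632.5 = 14.32 | −4.7% | 15.00 | −0.3% |
| 10% | 90/6615 = 13.61 | −9.5% | 14.96 | −0.5% |
| 20% | 80/6580 = 12.16 | −19.1% | 14.88 | −1.0% |
| 30% | 70/6545 = 10.70 | −28.9% | 14.80 | −1.6% |

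With 5% to 20% of patients having an event and u from 5% to 30%, the fall runs from 4.5% to 29.5%.

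**Second case.** Take a constant hazard of 20 per 1000 person-years and follow-up uniform over 3 to 15 years. Integrating the exponential gives, per patient, E = 0.1627, T1 = 0.801 and T0 = 7.335. The formula then gives:

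- u = 10%: 0.1464/8.056 = 18.2 (−9%)
- u = 20%: 0.1302/7.976 = 16.3 (−18%)
- u = 30%: 0.1139/7.896 = 14.4 (−28%)

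In simulation of this case, keeping undated events at the midpoint between discovery and last contact returns a rate within 0.2 of the true 20 for all three shares.

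**Between bands.** Keep the second case for the reference band and give the other band a hazard of 30 per 1000, a true ratio of 1.5. For that band E = 0.2325, T1 = 1.118 and T0 = 6.632.

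- Equal shares of 10% or 20%: the ratio is 1.51, almost unchanged.
- 10% undated in the reference band, 25% in the other: 23.3/18.2 = 1.28.
- The reverse: 27.4/15.4 = 1.78.

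**Other missing items.** Return to the simple case with u = 10%, and let a share f of event-free patients leave Cohort A for other reasons.

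- f = 0: 13.61
- f = 10%: 90/(5670 + 315) = 15.04, no net bias
- f = 20%: 90/(5040 + 315) = 16.81, an upward net bias

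**The case against.** The strongest case on the other side is that this is a missing data-handling rule and not a demonstrated bias. A reader might infer that the plan's CV rates will be too low. The documents do not support that, for these reasons:

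- **The date is requested.** It is among the minimum annotations, hospital records are the preferred source, and the questionnaire itself is not in the documents. Its described purpose is not a list of its fields. Nothing shows that any event will be undated.
- **Event-free patients also need a date.** They need a last follow-up date for censoring, and can fail Cohort A on hormone, imaging or comorbidity items. The last calculation shows that the net direction is not fixed.
- **Nobody leaves the study.** These patients move to Cohort B, which is also analysed. Its three items are a minimum, and no section says which cohort supplies ES or the CV rates. The cohort split is introduced in terms of patient characteristics, so applying it to an outcome date is one reading.
- **The scope is limited.** A CV death that is the first event is dated by the date of death. Section 2.3 describes telephone capture of major events only, although 2.4 is broader.

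All of this stands as a limit on the claim. What remains is that requesting a date does not say what happens when it is missing, and Cohort B exists because missing data are expected. An undated event cannot be timed for ES in either cohort as the plan is written, and this item can be missing only in patients who had the outcome. Any offset from other missing items would be fortuitous.

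**Conclusion.** The point holds in conditional form. Read literally, the Cohort A rule selects on the outcome for known but undated non-fatal first CV events, and the plan gives no alternative handling. This component lowers Cohort A CV rates by roughly the undated share. That share is not in the documents and may be zero. The effect on the ES hazard ratio is negligible when the share is similar across cortisol bands and material when it is not: 1.5 becomes 1.28 or 1.78 under an assumed 10% against 25%. The documents give no ground for expecting such a difference in either direction.

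The primary endpoint, OS, needs no CV date and is unaffected. The sizes rest on assumed event rates and follow-up, on no other missing items, and on whether an event is dated being unrelated to when it occurred. The point is worth correcting because CV events belong to the primary aim and the remedy is cheap, but it does not threaten the main OS analysis.

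**What to change.** 1. In the questionnaire and the annotation list (2.5), record the date of the first CV event to whatever precision is known: day, month, year, or an interval between two known dates.
2. In 2.4, state that a known event with a partial or missing date counts as an event and does not by itself remove the patient from Cohort A's CV analyses.
3. In the Kaplan-Meier and Cox analyses, place such an event at the midpoint between the last date known event-free (at earliest, discovery) and the contact date.
4. Add one sensitivity analysis, either interval-censored or using the earliest and latest possible dates.
5. Report the number of undated events by cortisol band.

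Interval censoring need not be the main analysis, since midpoint placement recovers the rate within ordinary Cox regression. The cost is one extra questionnaire field, one sensitivity analysis and approximate timing for the affected events. If no event proves to be undated, the results do not change.
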